12.1.4 Definitions for Statistical Data Analysis

The following definitions (**Table 19**) for statistical analyses/presentations will be used:

Table 19: Definition of terms for the statistical analysis

Term	Definition
Baseline Value	The last valid assessment prior to 06:30 AM on Day 1

For 24-hour urine collections, the collection sample will be labelled by the day in which the collection started. As an example if the 24-hour urine sample is collected from Day 5 to Day 6, it will be analyzed and reported as the Day 5 sample.

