9 STUDY ACTIVITIES

A detailed schedule of assessments can be found in [Appendix A](#).

The time points shown are to be considered the time of assessment for the first subject. As not all subjects can be treated at the same time, a short time window will be implemented for subsequent subjects. Measurements not conducted at the exact time point, but conducted within the given time window (if applicable) do not constitute a protocol deviation but an accepted variability for the given time point.

In general, if no start time for the procedure is provided, then the procedure can be performed at any time during the day.

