9.2.3 Exposure Period (Days 1 to 5)

Table 10 shows the assessments that will be performed on Day 1.

The collection of 24-hour urine of Day -1 starting on Day -1 will end on Day 1.

The collection of 24-hour urine sample for Day 1 will start on Day 1 and will end on Day 2.

Table 10 Time Schedule – Day 1

Time	Blood Sample	Procedures	Additional Information
Start of Procedure		Day 1	
6:30 AM		Start of use of IPs	
		AE/SAE recording	At any time of the day
		Concomitant medications	At any time of the day
		End of 24-hour urine sample collection for Day -1	The urine is collected for 24 hours \pm 1 hour. The end of the 24-hour urine collection should be prior to first use of IPs.

Confidentiality Statement

Data and information contained in this document are considered to constitute trade secrets and confidential commercial information, and the legal protections provided to such trade secrets and confidential information are hereby claimed under the provisions of applicable law. No part of this document may be publicly disclosed without the written consent of Philip Morris Products S.A.

Time	Blood Sample	Procedures	Additional Information
Start of Procedure		Day 1	
		Start of 24-hour urine sample collection for Day 1.	The start of 24-hour urine collection of Day 1 should be subsequent to the end of 24-hour urine collection of Day -1.
		Urine sample to be taken from the 24-hour urine of Day -1	Aliquots from 24-hour urine will be collected according to Table A2 . Bio-banking for biomarkers (if additional consent is obtained)
06:30 AM - 09:30 AM		Start of HPT assessment	In both study arms CHTP 1.0 and CC, the HPT SODIM® device has to be used for all smoking events when compatible CCs are smoked
Prior to 11:30 AM		Vital signs (blood pressure, pulse rate, respiratory rate)	At least 5 minutes in supine position
Prior to 11:30 AM		MNWS questionnaire	Has to be done prior to use of IPs
Prior to 11:30 AM		Assessment of cough (VAS)	Has to be done prior to use of IPs
In the evening prior to 9:00 PM (approx. 8:00 PM ± 1 hour)		CO breath test	Has to be done in conjunction with COHb blood sampling
In the evening prior to 9:00 PM (approx. 8:00 PM ± 1 hour)	√	COHb in blood	Has to be done in conjunction with CO breath test
In the evening prior to 9:00 PM (approx. 8:00 PM ± 1 hour)	√	Plasma nicotine and cotinine sample	Cotinine will be measured in the same assay as nicotine. No additional blood samples required
8:00 PM - 11:00 PM		Craving questionnaire (QSU brief)	

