12.1.2 Definitions for Statistical Data Analysis

Baseline:

Unless specified, baseline is defined as the last available time point prior to Day 1, 06:30 AM.

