7.2.4 Minnesota Nicotine Withdrawal Scale (revised edition) Questionnaire

The MNWS (**Hughes and Hatsukami 2008**) is a 24 hour recall that will be completed by the subject him/herself daily on Day -1 to Day 6 prior to product use to reflect the previous days experience. Therefore although it is collected on Days -1 to 6 it will be reported as Days -2 to 5.

The self-reported part of the MNWS, that was administered in this study consists of the following 15 items which are rated on a scale of 0 to 4 (see **Table 5**). Higher scores indicate greater intensity on that scale.

The total scores will be derived by calculating the average of all the non-missing data per Total Score as shown in **Table 5**. The first total score consists of the first 9 items, the second total score is based on 6 extra items which are thought to have an impact on withdrawal but have not been validated. If more than 50% of the items are missing then the total score will be set to missing.

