11.3 Assessment Windows

Smoking of the randomized products should take place within the 06:30 AM and 11:00 PM window.

The assessment windows are shown in **Table 16**.

Table 16: Assessment Windows

Assessment	Nominal Time point(s)	Window
24 h urine sample	Start (All days)	06:30 AM \pm 1 hour
	End on the following day (All days)	06:29 AM \pm 1 hour
CYP1A2 activity in plasma	Start (Days -1 and 5)	6 hours after intake of cup of coffee \pm 15 min
CYP2A6 activity	Day -1 and Day 6	Prior to smoking / product use
CO breath test	Day -2 to Day 5	In the evening prior to 09:00PM (approx 08:00 PM \pm 1 hour)
Assessment of Cough	Day -1 to 5	To be done prior to product use but not later than 11:30 AM
	Day 6	06:29 AM \pm 1 hour
MNWS questionnaire	Day -1 to 5	To be done prior to product use but not later than 11:30 AM
	Day 6	06:29 AM \pm 1 hour
QSU-brief questionnaire	Day -2 to 5	08:00 PM to 11:00 PM
MCEQ questionnaire	Day -2 to 5	08:00 PM to 11:00 PM
Nicotine and cotinine in plasma	Day -2 to Day 5	In the evening prior to 09:00PM (approx 08:00 PM \pm 1 hour)

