12.5.3.1.3 Minnesota Nicotine Withdrawal Questionnaire

The MNWS will be administered daily from Days -1 to 6 for the assessment of Day -2 to Day 5 as it is a 24-hour recall questionnaire. The baseline will be the last assessment prior to 06:30 AM on Day 1.

All summaries, profiles and analysis will be presented for the CHTP and CC arms.

The change from baseline will be calculated for both scores. The two scores, along with the change from baseline will be summarized. The answers to the individual questions, along with the two scores and changes from baseline will be listed.

The profiles of the raw means from baseline to Day 6 for the total scores will be produced.

The analysis will compare each post baseline timepoint for the two scores. A repeated measures ANCOVA model will be used with terms for baseline score, sex, average daily CC consumption over the last 6 weeks as reported during screening, product, time-point, and the interaction between product and time-point.

The SAS code will be the same as described in Section 12.5.3.1.1 “Urge-to-Smoke Questionnaire of Smoking Urges Brief”.

LS means for each product along with the difference (CHTP - CC) with 95% CI will be presented in the tables.

All figures, summaries and analyses will be performed on the FAS.

The data will be presented in the below outputs, the TFL number refers to the TFL number in the accompanying TFL shell document:

TFL number	Title
TABLES	
15.2.4.22	Descriptive Statistics of MNWS Total Scores – FAS
15.2.4.23	Analysis of MNWS Total Scores – FAS

TFL number	Title
FIGURES	
15.1.2.33	MNWS Total Scores Arithmetic Mean and 95% CI – FAS
15.1.2.34	MNWS Total Scores Arithmetic Least Squares Means and 95% CI – FAS
LISTINGS	
15.3.6.12	Listing of MNWS Questionnaire Results and Changes from Baseline

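### The 06:30 AM Day 1 baseline cut-off can reject a pre-switch MNWS form that the assessment window still allows, so the MNWS baseline day depends on clock time

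*SAP*

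**What the plan says.** The general baseline in SAP 12.1.4 (Table 19) is "The last valid assessment prior to 06:30 AM on Day 1". Protocol 12.1.2 uses the same cut-off: unless specified otherwise, "baseline is defined as the last available time point prior to Day 1, 06:30 AM". SAP 12.5.3.1.3 restates it for the MNWS: "The baseline will be the last assessment prior to 06:30 AM on Day 1".

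The MNWS window for Days -1 to 5 in SAP 11.3 (Table 16) is "To be done prior to product use but not later than 11:30 AM". Protocol 9.2.3 (Table 10) gives the Day 1 form the same 11:30 AM limit and adds "Has to be done prior to use of IPs". Protocol section 9 says of its schedules that "The time points shown are to be considered the time of assessment for the first subject", with a window for subsequent subjects.

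The MNWS is a 24-hour recall. SAP 7.2.4 therefore shifts the day label: "although it is collected on Days -1 to 6 it will be reported as Days -2 to 5". SAP 12.5.3.1.3 fits a repeated measures ANCOVA to the post-baseline time points with the baseline score as a covariate. SAP section 9 makes the comparison across all time points the main one. SAP 5.3 defines the MNWS endpoint as Day 1 to Day 5.

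**The concern.** The baseline rule works by clock time. The assessment window works by order: the form must come before product use. On Day 1 the two can disagree. A form completed at 07:00 by a subject who has not yet used the product is compliant and describes a period spent entirely on CC, but it misses the cut-off by half an hour.

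Two things follow for such a subject. The baseline covariate, and any change from baseline, comes from the form collected on Day -1, which recalls Day -2. For a subject who completes the form at 06:15 it comes from the Day 1 form, which recalls Day -1. The baseline day then differs between subjects for no reason linked to exposure. In addition, the 07:00 form falls after baseline, so a literal programmer could enter it in the repeated measures model as a post-baseline time point, although no product effect can yet exist.

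**Working it through.** The plan gives no figure on this point (no share of late forms, no expected MNWS effect), so there is none to reproduce.

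**1. What each form describes** (SAP 7.2.4)

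| Collected on | Reported as | Product during recall |
|---|---|---|
| Day -1 | Day -2 | CC in both arms |
| Day 1, before product use | Day -1 | CC in both arms |
| Days 2 to 6 | Days 1 to 5 | Assigned product |

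**2. Overlap of the window and the cut-off.** The Day 1 window closes at 11:30 AM and the baseline rule closes at 06:30 AM. The part of the window that fails the rule is 11:30 - 06:30 = 5 hours = 300 minutes. Late forms are foreseeable: the scheduled times are those of the first subject, and product use may start only from 06:30 and only after the Day -1 urine collection has ended.

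**3. Two compliant subjects**
- Form at 06:15: baseline is the Day 1 form. Five forms follow, all post-switch.
- Form at 07:00: baseline is the form collected on Day -1. Six forms follow, one of them pre-switch.

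**4. Effect on the averaged CHTP-CC difference.** Let d be the true difference, assumed constant over reported Days 1 to 5 and zero on reported Day -1. Let f be the share of Day 1 forms timed at or after 06:30, assumed unrelated to arm. The documents do not give f.

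(a) *Product-by-time interaction kept, time points weighted equally in the LS means, late forms entered as a sixth time point:* estimate = (5d + 0)/6 = 0.833d, a dilution of 1/6 = 16.7%. This does not depend on f, as long as some late forms in each arm make the sixth level estimable.

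(b) *Each subject averaged over his or her own forms, as an approximation if the interaction is dropped:* estimate = (1 - f)d + f(5/6)d = (1 - f/6)d.

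| f | Multiplier of d | Dilution |
|---|---|---|
| 0 | 1.00 | 0% |
| 0.25 | 0.96 | 4% |
| 0.50 | 0.92 | 8% |
| 1 | 0.83 | 17% |

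(c) *Reported Day -1 kept out of the model, following the endpoint definition in SAP 5.3:* estimate = d, with no dilution. Only the mixed baseline day remains.

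The text does not settle between (a) and (b). SAP 12.5.3.1.3 lists the interaction without a removal rule but borrows its code from SAP 12.5.3.1.1, where the interaction is dropped at p > 0.1.

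**The case against.** The best defence is that the day label settles the matter. SAP 12.5.3.1.3 says that the forms collected on Days -1 to 6 assess Days -2 to 5, and the baseline sentence comes straight after. On that reading the Day 1 form is the Day -1 assessment, lies before the cut-off, and is the baseline. The endpoint definition of Day 1 to Day 5 likewise excludes a sixth time point. This probably shows the intention, and it is why the dilution may be nil. But a clock time belongs to the completion of a form, not to a recalled day, and no text says that the label overrides it. The same section also describes profiles running to Day 6, which is a collection day, so it mixes the two day systems.

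A second defence is that 06:30 is a sound general cut-off. It is the defined start of the Exposure Period, and subjects learn their arm shortly before it. A general baseline tied to first product use would hang on a time that the subject chooses after learning the allocation. That stands, and the general rule should be left alone.

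A reader might also infer that urine baselines for three primary endpoints are at risk. The Day -1 collection may end between 05:29 and 07:29 on Day 1, and 60 of those 121 minutes fall at or after 06:30, which suggests that about half of subjects would fall back to Day -2. The documents do not support this. SAP 12.1.4 has each collection analysed and reported under its start day. Table A2 places the Day -1 collection in the Baseline Period. Nothing applies the cut-off to a collection's end time. Both collections are in any case pre-switch, so even that reading would change only covariate precision.

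**Conclusion.** The point holds for the MNWS. As written, the rule gives a different baseline day to any subject whose compliant Day 1 form is timed at or after 06:30, and it leaves open whether that pre-switch form is analysed as post-baseline.

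The dilution of the averaged difference runs from 0 to about 17%. The upper end should not be read as the expected size. It needs reported Day -1 to enter the model despite the endpoint definition, together with either equal weighting of six time points or all forms late. It also assumes a constant effect after the switch.

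The consequence is confined to an exploratory questionnaire. COHb, exhaled CO, plasma nicotine and cotinine, QSU-brief and MCEQ have evening assessments on Day -1 and are untouched. The cough assessment shares the MNWS window, but SAP 12.5.4.5.6 plans summaries by day with no change from baseline. No primary analysis is affected.

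**What to change.** In SAP 12.5.3.1.3, state that:
- the MNWS baseline is the form completed on Day 1 before product use (reported as Day -1), whatever its clock time;
- the repeated measures model uses reported Days 1 to 5 only.

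The same edit should say which form is used if the Day 1 form is missing or was completed after product use (the form collected on Day -1 is the natural fallback), and should put the profile plots on the reported-day scale.

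Record the exception to the 06:30 rule in SAP section 9. Protocol 12.1.2 allows a baseline to be specified differently. Leave the general definition in SAP 12.1.4 unchanged for other endpoints.

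The cost is a few sentences in the SAP before database lock. No data collection, schedule or sample size changes.

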12.1.5 Handling of Dropouts or Missing Data (including outside the limits of quantification)

For questionnaire data total scores and domain or subscale scores may use a certain degree of imputation (by averaging across individual item scores) as detailed in Section 7.2 "Questionnaires".

In general, values below the Lower Limit of Quantification (LLOQ) will be imputed using LLOQ/2. For values above the Upper Limit of Quantification (ULOQ) i.e., preceded by a “>”, for example “>xx”, the numerical xx will be used for calculation and reporting in summary tables. The number of values below LLOQ or above ULOQ will be presented in each summary table.

12.1.5.1 Insufficient Data for Analysis/Presentation

If there are no values/events at the general value then the break out should not be presented. For example if the number of related AEs is zero then no presentation by severity of related events at the single level will be produced.

Some of the TFLs will not have sufficient numbers of subjects or data for presentation. If this occurs, the blank TFL shell will be presented with a message printed in the center of the table, such as, “No serious adverse events occurred for this study.”

Stratified summaries by sex or daily CC consumption will not be presented if less than 4 subjects are available in one sex or nicotine levels strata.

12.1.6 Handling of Unplanned Data

Unscheduled readings will be excluded from the summary statistics. Unscheduled readings will be labelled as unscheduled in the listings and mapped to the study day using the date of the study day until midnight.

12.1.7 Multiple Comparisons / Multiplicity

Unless stated otherwise, all statistical tests will be two-sided and conducted at the 5% level, and all quoted confidence intervals (CIs) will be two-sided 95% CIs.

The primary endpoints will be tested using a multiple testing procedure (**EMEA Points to consider on multiplicity issues in clinical trials**) to preserve the overall alpha level by simultaneously testing the endpoints using a closed procedure with each test performed at a two-sided alpha level of 5%.

No adjustment for multiplicity will be made on any of the secondary endpoints.

12.2 Disposition of Subjects

The number and percent of subjects will be summarized for the following categories: subjects screened, enrolled subjects, exposed and not randomized, randomized subjects, completed, and discontinued (if applicable discontinued subject that never used their allocated products will be identified).

All subjects who screenfail or discontinue the study will be categorized by their primary reason for screen failure or discontinuation. Disposition of subjects and reasons for withdrawal will also be summarized separately. Supportive listings will be provided.

The number and percent of randomized subjects with protocol deviations and the number of protocol deviations will be summarized by product, broken down by main deviation category (major/minor) and sub-categories. Subjects will be counted once per deviation category, and can be counted for more than one deviation category.

Supportive listings will be provided, including any additional comments for tests that are not performed to be included on the listings of individual data.

The data will be presented in the below outputs, the TFL number refers to the TFL number in the accompanying TFL shell document:

TFL number	Title
TABLES	
15.2.1.1	Summary of Subject Disposition – All Screened Subjects
15.2.1.2.1	Summary of Reasons for Screen Failure – All Screened Subjects
15.2.1.2.2	Summary of Reasons for Discontinuations – All Enrolled Subjects
15.2.1.3	Summary of Protocol Deviations – FAS
LISTINGS	
15.3.1.1	Listing of Inclusion/Exclusion Criteria
15.3.1.8	Listing of Subject Disposition, Randomization and Assignment to Analysis Sets
15.3.1.11	Listing of Protocol Deviations
15.3.2.2	Listing of Subject and Observations Excluded from Efficacy Analysis
16.1.7	Listing of Randomization Schemes and Codes

12.3 Demographics and Other Baseline Characteristics

Demographic and baseline characteristics will be summarized for the Safety Population, FAS and PP, and listed for all screened subjects.

The demographic variables age, sex, race, body weight, height and BMI will be summarized by exposure, and by sex and CC consumption. Other baseline characteristics and Current CC brand(s) at Admission will also be included in the table.

No inferential analyses will be presented for the demographic and baseline characteristics.

The data will be presented in the below outputs, the TFL number refers to the TFL number in the accompanying TFL shell document:

TFL number	Title
TABLES	
15.2.1.4.1	Summary of Demographics and Other Baseline Characteristics – Safety Population
15.2.1.4.2	Summary of Demographics and Other Baseline Characteristics – FAS
15.2.1.4.2.1	Summary of Demographics and Other Baseline Characteristics by Sex – FAS
15.2.1.4.2.2	Summary of Demographics and Other Baseline Characteristics by Cigarette Consumption – FAS
15.2.1.4.3	Summary of Demographics and Other Baseline Characteristics – PP
LISTINGS	
15.3.1.7	Listing of Demographics

12.3.1 FTND Questionnaire at Screening

FTND score value and the number and percentage of subjects in each category (mild/moderate/severe) will be presented. Data will be listed and summarized as part of the demographics and baseline characteristics (Section 12.3).

The data will be presented in the below outputs, the TFL number refers to the TFL number in the accompanying TFL shell document:

TFL number	Title
TABLES	
15.2.1.4.1	Summary of Demographics and Other Baseline Characteristics – Safety Population
15.2.1.4.2	Summary of Demographics and Other Baseline Characteristics – FAS
15.2.1.4.2.1	Summary of Demographics and Other Baseline Characteristics by Sex – FAS
15.2.1.4.2.2	Summary of Demographics and Other Baseline Characteristics by Cigarette Consumption – FAS
LISTINGS	
15.3.1.10	Listing of Fagerström Test for Nicotine Dependence Results

12.3.2 Current Cigarette Brand and Smoking Characteristics

The following smoking characteristics at Admission (Day -2) will be summarized and listed as specified in Section 12.3. ISO tar yields (continuous and categorized as 1-5 mg, 6-8 mg, 9-10 mg and > 10 mg), ISO nicotine level (continuous and categorized as ≤ 0.6 mg and > 0.6 to ≤ 1 mg), and number of CCs smoked on a daily basis during the previous 6 weeks and since the subject started smoking (continuous and categorized as 10-19 CC/day and >19 CC/day).

Current CC brand(s) smoked by the subject and recorded at Admission (Day -3) will be summarized and listed by product for the FAS. This will include brand name(s) and ISO nicotine, tar, and CO yields. Data at screening will be listed only.

Smoking history, including whether subjects have smoked for at least the last three years, number of years smoked, whether the subject used any nicotine containing products other than commercially available non-menthol CC within 6 weeks prior to admission, and e-cigarette use over the last year will be listed by product at Screening and Admission (Day - 2) where applicable. Responses to planning to quit smoking during the next 3 months will be listed at Screening.

Data will be listed and summarized as presented in the below outputs, the TFL number refers to the TFL number in the accompanying TFL shell document:

TFL number	Title
TABLES	
15.2.1.4.1	Summary of Demographics and Other Baseline Characteristics – Safety Population
15.2.1.4.2	Summary of Demographics and Other Baseline Characteristics – FAS
15.2.1.4.2.1	Summary of Demographics and Other Baseline Characteristics by Sex – FAS
15.2.1.4.2.2	Summary of Demographics and Other Baseline Characteristics by Cigarette Consumption – FAS
15.2.1.5	Summary of Current Cigarette Brands – FAS
LISTINGS	
15.3.1.2	Listing of Current Cigarette Brands
15.3.1.3	Listing of Smoking History
15.3.1.4	Listing of Advice on Risks of Smoking / Smoking Cessation
15.3.1.5	Listing of Product Test

12.3.3 Medical History and Concomitant Diseases

Medical history is defined as any condition that started and ended prior to Screening. Medical history will be coded using MedDRA version 18.0 and listed separately by product, System Organ Class (SOC) and Preferred Term (PT) within SOC.

Medical History will be summarized by product, SOC and PT for the FAS.

Concomitant disease is defined as any condition diagnosed at Screening or was ongoing at Screening. Concomitant disease will be coded using MedDRA version 18.0 and listed separately by product, SOC and PT within SOC.

Concomitant disease will be summarized by product, SOC and PT for the FAS.

Partial dates will not be imputed, but assumptions will be made as follows to assign to either medical history or concomitant diseases:

Date information	Assign as
Missing stop date	Concomitant disease
Partial date, e.g. --May2012, or ----2011. If month/year is the same as, or later than the month and/or year of Screening.	Concomitant disease
Partial date, e.g. --May2012, or ----2011. If month and/or year is earlier than the month and/or year of Screening.	Medical history

The data will be presented in the below outputs, the TFL number refers to the TFL number in the accompanying TFL shell document:

TFL number	Title
TABLES	
15.2.1.6	Summary of Medical History – FAS
15.2.1.7	Summary of Concomitant Diseases – FAS
LISTINGS	
15.3.1.9	Listing of Medical History and Concomitant Diseases

